Kasr Alainy & Eyecare center, Maadi, Cairo.(ETDRS chart, Pelli Robson illuminated chart, OPD scan being not available at Kasr Alainy hospitals).

- Inclusion criteria:

- Patients aged more than 50-75 years old undergoing cataract surgery.
- Preoperative corneal astigmatism equal to or less than 0.75 D.

- Exclusion criteria:

- Other ocular comorbidities such as glaucoma, corneal opacities, chronic or recurrent anterior uveitis, diabetic retinopathy, age -related macular degeneration.
- Previous ocular surgeries.
- Undergoing combined surgeries.

Methodology in details:

40 eyes of 20 patients will be included in this prospective study. The Tecnis® Eyhance IOL will be implanted in 20 eyes of 10 patients (group 1), and 20 eyes of 10 patients will be implanted with Tecnis® 1-piece (group 2).

Preoperative assessment:

All selected patients will receive thorough explanation of the study design and aims, and an informed consent will be obtained from all patients.

Eyes before intervention will be subjected to:

- Measurement of uncorrected and best-corrected distance visual acuity using ETDRS chart.
- Slit lamp examination.
- Measurement of intraocular pressure using applantation tonometer.
- Dilated fundus examination using binocular indirect slit lamp biomicroscopy.
- Specular microscopy .

Cairo University

KASR ALAINY
CAIRO UNIVERSITY - FACULTY OF MEDICINE

- Optical biometry using (IOLMaster 500; Carl Zeiss Meditec AG, Jena, Germany) and using online Barrett's universal formula. With target refraction of 0 or +0.25 D in the Eyehance group While in the Tecnis group the dominant eye will be aimed at 0 D and the non-dominant eye for -0.5 D.

Surgical intervention:

Surgery will be performed under topical anaesthesia using topical Benoxinate or local anaesthesia using peribulbar Lidocaine injection.

- Speculum used to maintain lids open.
- Clear corneal incision placed superotemporally using 2.2 mm keratome and paracenteses are placed using 15 superblade at 90 degrees to the main wound.
- Followed by formation of anterior chamber using Ophthalmic Viscoelastic Device (hydroxypropyl methylcellulose).
- Continuous curvilinear capsulorrhesis is created using straight sharp tipped Uttrata's capsulorrhesis forceps aiming at 5 mm size.
- Phacoemulsification of nucleus
- Bimanual irrigation and aspiration of cortical material.
- Injection of Ophthalmic Viscoelastic Device to form anterior chamber and inflate the capsular bag.

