Uncorrected and best-corrected distance, and intermediate visual acuity.

Cairo University

KASR ALAINY
CAIRO UNIVERSITY - FACULTY OF MEDICINE

- Secondary outcome parameters (other outcomes to be assessed)

- 1) contrast sensitivity.
- 2) Photic phenomena.
- 3) Spectacle independence.

10- Sample size (number of study subjects included and justification including the clinical and statistical assumptions supporting sample size calculation)

With a sample size of 18 (9/group), we will have a power of 95% to assess whether the mean logMAR For UIVA is significantly lower in the new monofocal IOL (~0.16 +/-0.06) compared to the standard monofocal IOL with a mean logMAR for UIVA Of ~0.27 (0.06), using a 2 samples means test and a significance level of 0.05

11- Statistical analysis (Please describe your data analysis plan)

Statistical plan

Summary statistics will be done, categorical variables would be presented as frequency and percentages and numerical ones as mean (SD) or median (IQR) as appropriate.

Comparison between the two groups will be done using the Students t test or the Wilcoxon rank sign test according to data normality. The Chi squared test will be used to compare categorical variables. P<0.05 will be considered significant. STATA 15.1 will be used for the analysis.

12- Source of funding: (Please include source of funding even if self funding)

- Faculty of Medicine, Cairo University

Cairo University

KASR ALAINY

CAIRO UNIVERSITY - FACULTY OF MEDICINE

- Other sources:

Please specify: self funding

13- Time plan:

- When to start?
Just after thesis registration
- When expected to finish?
within 6 months or as soon as number of participants has been reached.
- When to publish? As soon as results are available.

14- References:

1. Jafarinab, M. R., Feizi, S., Baghi, A. R., Ziae, H., & Yaseri, M. (2010). Aspheric versus spherical posterior chamber intraocular lenses. *Journal of ophthalmic & vision research*, 5(4), 217.
2. Unsal, U., & Sabur, H. (2020). Comparison of new monofocal innovative and standard monofocal intraocular lens after phacoemulsification. *International Ophthalmology*, 1-10.
3. de Silva, S. R., Evans, J. R., Kirthi, V., Ziae, M., & Leyland, M. (2016). Multifocal versus monofocal intraocular lenses after cataract extraction. *Cochrane Database of Systematic Reviews*, (12).

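### Section 11 names a Wilcoxon test that reads as the paired signed-rank test, but the two lens groups are different, unmatched patients; it should name the rank-sum (Mann-Whitney) test

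*Combined protocol and SAP*

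**What the plan says.** Section 11 gives one rule for comparing numerical outcomes between the lens groups: "Comparison between the two groups will be done using the Students t test or the Wilcoxon rank sign test according to data normality". It names STATA 15.1 as the software. No other nonparametric test for two groups appears in the document.

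The design is described under Methodology in details (Section 7). In total, "40 eyes of 20 patients will be included in this prospective study". For the new lens, "The Tecnis® Eyhance IOL will be implanted in 20 eyes of 10 patients (group 1"); for the comparator, "20 eyes of 10 patients will be implanted with Tecnis® 1-piece (group 2"). Ten plus ten makes the 20 patients enrolled, so no patient is in both groups. No matching of patients across groups is described.

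Section 10 justifies the sample size for uncorrected intermediate acuity at 9 per group, "using a 2 samples means test and a significance level of 0.05".

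**The concern.** A signed-rank test needs a natural partner for each observation, and this design has none across the lenses. The only natural pair is a patient's two eyes, and both eyes carry the same lens, so that pair cannot inform a comparison between lenses. An analyst who follows the words as written must pair patients from one group with unrelated patients from the other, in practice by row order. Two analysts with the same data in a different order could then report different p-values. If dropout leaves the groups unequal, the surplus patients have no partner and are lost from the test.

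The sentence governs the primary outcomes. Section 7 has intermediate acuity read from a Jaeger chart, recorded as decimals and converted to logMAR. A stepped chart can give discrete, tied values, so the non-normal branch could plausibly be reached for the outcome on which the study is powered.

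**Working it through.** **Inputs.** From Section 10: mean logMAR 0.16 (new lens) and 0.27 (standard lens), SD 0.06 in each, 9 per group, alpha 0.05, stated power 95%. From Section 7: 10 patients per group planned. Sidedness is not stated; two-sided is assumed here.

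**Step 1: reproduce the plan's figure and see which design it implies.** The difference is 0.27 − 0.16 = 0.11.

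- *Unpaired t test, 9 per group.* Noncentrality = (0.11/0.06) × √(9/2) = 1.833 × 2.121 = 3.889, with 9 + 9 − 2 = 16 degrees of freedom and critical value 2.120. Power = **95.4%**, which matches the stated 95%. The sample size that solves for 95% is 8.82, rounded up to 9.
- *Paired t test, 9 uncorrelated pairs.* SD of a within-pair difference = 0.06 × √2 = 0.0849. Noncentrality = 0.11/0.0849 × √9 = 3.889, the same, but with only 8 degrees of freedom and critical value 2.306. Power = **92.4%**.

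The sample size therefore treats the groups as independent. Section 11, read literally, does not.

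**Step 2: what the literal fallback does under the plan's inputs.** Normal data, SD 0.06, 10 per group, 40,000 simulated data sets per difference. The exact signed-rank test on one random pairing is compared with the exact rank-sum test, two-sided 0.05. Only the 0.11 row uses the plan's difference; 0.06 and 0.05 are assumptions.

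| True difference | Same verdict | Rejection rate, signed-rank | Rejection rate, rank-sum |
|---|---|---|---|
| 0.11 (plan) | 96.0% | 94.1% | 95.7% |
| 0.06 | 86.3% | 49.7% | 51.3% |
| 0.05 | 86.9% | 37.5% | 38.1% |
| 0 (type I error) | not tabulated | 4.9% | 4.3% |

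At the 9 per group used in Section 10, with the 0.11 difference, agreement is 92.7% and power is 88.7% against 92.9%.

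**Step 3: dependence on row order.** In one simulated data set of 10 per group (means 0.20 and 0.27, SD 0.06), the rank-sum p-value is a single number, 0.0007. Over 3,000 random pairings of the same data, the signed-rank p-value ran from 0.002 to 0.027. All were significant in that instance, but the reported value is arbitrary. At the planned difference, the share of data sets in which some tried pairings reach significance and others do not is 21% with 60 pairings, 28% with 500 and 33% with 3,000. That share grows with the number tried and is not the chance of a wrong verdict.

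**Step 4: non-normal data, where the fallback would apply.** The documents give no outcome distributions, so these shapes are assumptions. Difference 0.11, 10 per group, 6,000 data sets each, large-sample tie-adjusted tests:

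| Assumed shape | Same verdict | Power, signed-rank | Power, rank-sum | Loss (points) |
|---|---|---|---|---|
| Exponential skew | 93.6% | 92.4% | 97.4% | 5.0 |
| Normal, rounded to 0.1 logMAR | 93.5% | 89.5% | 93.1% | 3.6 |
| Skewed and rounded | 89.1% | 84.8% | 92.1% | 7.3 |

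Signed-rank type I error stayed at 4.8–5.0%. A separate run on assumed shapes of this kind gave agreement of about 90–93% and losses of about 6–9 points; the result depends on how zero differences are handled.

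**The case against.** The strongest reply is that this is a naming slip. *Rank sign* is one word from *rank sum*, and everything around it is two-sample: the sentence compares two groups, the test is offered as the alternative to Student's t test, and the sample size is unpaired. An analyst with no pairing variable would notice the mismatch and probably run the rank-sum test. Harm requires that normality is rejected, that the phrase is read as signed-rank, and that unrelated patients are then paired. Even so, the verdict changes in only about 4% of data sets at the planned difference, in both directions, and the t test branch is unaffected. If the analysis were run on 20 eyes per group treated as independent, agreement would be 99.96%.

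Much of this stands. A slip is plausible, the use of the fallback cannot be quantified, and the loss at the planned difference is small. The figure for 20 eyes per group carries less weight, because it ignores correlation between a patient's two eyes. None of this makes the wording correct. A prespecified test should not have to be guessed, and STATA has separate commands for the two candidates (`signrank` and `ranksum`), with the written words pointing to the wrong one. A silent switch to rank-sum at analysis would also look like an undocumented deviation.

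**Conclusion.** The concern holds: the nonparametric test is wrong as written for two independent groups, and it sits in the operative sentence for the primary comparison. The consequence is an arbitrary p-value and some loss of power, without material inflation of type I error. At the plan's own difference and 10 per group, the power loss is 95.7 − 94.1 = 1.6 points. It is about 4 to 9 points under the assumed non-normal shapes. These figures apply only if the fallback is triggered and taken literally. The stated sample size and the t test are unaffected. This should be corrected before analysis; it does not threaten the trial's validity.

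**What to change.** In Section 11, replace the *rank sign* wording for the between-group comparison with the Wilcoxon rank-sum (Mann-Whitney) test, run with `ranksum` rather than `signrank` in STATA. This makes Section 11 consistent with Section 10. It costs one phrase, changes no data collection or sample size, and has no downside.

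Correlation between a patient's two eyes in one-eye outcomes is a separate issue that this change does not resolve.

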- Implantation of Eyehance or Tecnis® 1-piece intraocular lens in capsular bag.
- Irrigation and aspiration of Ophthalmic Viscoelastic Device.
- Injection of intracameral moxifloxacin in the capsular bag and hydration of self-sealing clear corneal incisions.

Post-operative:

All patients will receive a topical antibiotic (moxifloxacin) and steroids (Prednisolone acetate) eyedrops in a slow tapering course over 4 weeks.

Follow up:

Cairo University

KASR ALAINY

CAIRO UNIVERSITY - FACULTY OF MEDICINE

All patients will be examined at day 1, 1 week and 1 month and 3 months postoperative.

At three months follow up all patients will be evaluated regarding:

- Corrected and uncorrected distance (at 6 meters) and intermediate (at 66cm) vision both unocular and binocular.
- Photopic contrast sensitivity using Pelli Robson chart illuminated chart with controlled ambient illumination
- Mean binocular defocus results will be measured and defocus curves of the two lenses will be created.
- A questionnaire to evaluate the photic phenomena and spectacle independence will be explained and filled by the patients.

Distance visual acuities will be examined by ETDRS chart and intermediate and near visual acuity by Jaeger chart at 66 cm and 33 cm respectively

Measured values of the visual acuity will be expressed in decimal values and will be converted to logMAR values.

- **Intervention:**

- Diagnostic intervention (please describe):
- Therapeutic intervention (please describe): phacoemulsification, Eyhance IOL or TECNIS 1-piece IOL implantation.
- No intervention

Both diagnostic and therapeutic.

- **Does the research involve?**

- Human participants

Cairo University

KASR ALAINY
CAIRO UNIVERSITY - FACULTY OF MEDICINE

Biological samples/Tissues

Identifiable private data/Information

- **Type of consent of study participants:**

Written consent
 Oral consent
 No consent needed (Please justify)

- **Potential risks:**

(Please mention all risks involved even mild ones as pain, discomfort, chance of infection or psychological effects)

- 1- Risks related to surgical intervention including corneal oedema, infection, retinal detachment, hemorrhage, IOL displacement, elevated intraocular pressure, optic atrophy,
- 2- Risks related to intraocular lens including photic phenomena as halos and glare.

- **Confidentiality of data:** will be maintained in a secure file with the investigators.

9- Study outcomes:

- **Primary outcomes** (Most important measurable outcomes)

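### If the questionnaire items are graded, the only test named for categorical variables ignores the order of the grades and gives up power on two secondary outcomes

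*Combined protocol and SAP*

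**What the plan says.** Section 11 (Statistical analysis) sets two rules for comparing the groups. For one set of variables, "Comparison between the two groups will be done using the Students t test or the Wilcoxon rank sign test according to data normality". For the other, "The Chi squared test will be used to compare categorical variables". Summaries follow the same split: "categorical variables would be presented as frequency and percentages and numerical ones as mean (SD) or median (IQR) as appropriate". The threshold is "P<0.05 will be considered significant". No trend, rank or exact test is named for categorical variables.

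The answers at issue are collected at three months (section 7, Follow up): "A questionnaire to evaluate the photic phenomena and spectacle independence will be explained and filled by the patients". No instrument, list of items or response scale is given. Section 9 lists "Photic phenomena" and spectacle independence as secondary outcomes, beside contrast sensitivity. Section 7 plans 10 patients (20 eyes) per lens group. The power statement in section 10 concerns uncorrected intermediate visual acuity (UIVA) only.

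**The concern.** Halo, glare and spectacle use can be asked as yes/no or in grades, such as none to severe or never to always. On graded answers the chi-squared statistic is the same however the grades are ordered. A consistent move towards milder grades therefore counts no more than a haphazard scatter of the same size, and the test spends k − 1 degrees of freedom on k grades. A rank-sum test on the same answers uses the order.

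What is at stake is power, not the false-positive rate. Section 4 partly justifies the new lens by its low level of photic phenomena. Whether patients are better or worse off on these items is a directional question, and there are only 20 patients to answer it.

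**Working it through.** **The plan's own figure.** Section 10 gives 9 per group and 95% power for UIVA: means 0.16 and 0.27 logMAR, SD 0.06, significance level 0.05. The non-centrality is 0.11 / (0.06 × √(2/9)) = 3.89 on 16 degrees of freedom. A two-sided t test then has 95.4% power, so the figure reproduces. The documents give no power or effect size for any categorical outcome, so everything below rests on assumed inputs.

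**Inputs.** From the documents: 10 patients per group and a 0.05 threshold (two-sided assumed). Assumed: 3 to 5 ordered grades, the control-group distribution, and a proportional-odds shift with odds ratio (OR) 3, 5 or 8.

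**Formulas.** Let a_j and b_j be the counts in grade j, t_j = a_j + b_j, n = 10 and N = 20.
- Chi-squared: X² = Σ (a_j − b_j)² / t_j, with df = non-empty grades − 1.
- Rank-sum: W = Σ a_j × (mid-rank of grade j), with mean n(N + 1)/2 = 105 and variance (n²/12) × [(N + 1) − Σ(t_j³ − t_j) / (N(N − 1))].

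**One invented table, to show the mechanism.** Counts from best to worst grade are 6, 3, 1, 0 against 2, 3, 2, 3.
- Chi-squared: X² = 16/8 + 0/6 + 1/3 + 9/3 = 5.33 on 3 df, p = 0.15.
- Rank-sum: mid-ranks are 4.5, 11.5, 16 and 19, so W = 27 + 34.5 + 16 + 0 = 77.5. The tie sum is 504 + 210 + 24 + 24 = 762 and the variance is (100/12) × (21 − 762/380) = 158.3. So z = (77.5 − 105)/12.58 = −2.19, p = 0.029.

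**Power at OR 5.** All 10 v 10 tables were enumerated and weighted by their probabilities. For 4 even grades, OR 5 moves the cumulative proportions 0.25, 0.50, 0.75 to 0.625, 0.833, 0.9375. The loss is 1 − (chi-squared power / rank-sum power).

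| Control distribution (%) | Ordinary tests: chi-squared v rank-sum | Loss | Exact versions | Loss |
|---|---|---|---|---|
| 3 even | 30.8% v 43.6% | 29% | 29.6% v 34.1% | 13% |
| 4 even | 27.8% v 45.9% | 39% | 29.7% v 41.4% | 28% |
| 4 skewed (50/30/15/5) | 18.5% v 36.4% | 49% | 20.5% v 25.3% | 19% |
| 5 even | 22.4% v 46.9% | 52% | 27.8% v 44.5% | 37% |
| 5 skewed (40/30/15/10/5) | 18.1% v 41.5% | 56% | 23.9% v 33.5% | 29% |

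**Range over OR 3 to 8, ordinary tests.** The smallest loss is about a fifth (3 grades, control mostly severe, OR 8: 53% v 65%). The largest is about three fifths (5 grades with a central peak, 10/20/40/20/10, OR 3: 9% v 25%).

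**Exact versions.** The loss is about 6 to 41%. The centrally peaked 5-grade case lies somewhat above this, at 46% for OR 3 (12.3% v 22.6%).

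**Absolute power at OR 3, ordinary tests.** About 9 to 17% for chi-squared against 17 to 26% for rank-sum.

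**Size with no difference.** 2.8 to 4.8% for chi-squared and 4.7 to 5.0% for rank-sum, so the extra power does not come from excess false positives.

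**Two grades.** The two tests agree exactly (both 31.5% at OR 5, even split), so the loss is zero.

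**Expected counts.** With equal groups, the average expected count is 20/(2k): 3.3, 2.5 and 2 for k = 3, 4 and 5. For a yes/no item the rarer answer has expected count (its total)/2 per group, which is below 5 unless the answers split exactly 10 to 10.

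**The case against.** The strongest reply is that the documents never say the answers are graded. Spectacle independence in particular could be a single yes/no item, and then nothing is lost. This stands. A reader might infer that the plan as written forfeits a stated share of its power; the documents do not support that, because the share depends on a scale, a distribution and an effect that they do not give.

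Nor is it settled that graded answers would go to chi-squared. If scored as numbers, they could fall under the sentence on the t test and Wilcoxon test. That also stands, but it is not a safeguard: the choice is left open until the answers are seen, and the Wilcoxon *rank sign* test as printed reads as the paired signed-rank test, which does not suit two separate groups.

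Part of the loss is small-sample conservatism of the ordinary chi-squared test and not lost ordering; the exact columns show this. The ordinary test is the one section 11 names, though, and the rank-sum test keeps an advantage in every directional scenario examined.

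Power is low with either test at OR 3, and section 4 expects the two lenses to have similar photic profiles. Both are fair. A better test does not make the study adequate for modest effects, and a non-significant result from either test would not show similarity.

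Finally, chi-squared does better when the groups differ in spread and not in direction. With 25/25/25/25% against 2/48/48/2%, the exact tests have 42% power against 5% for rank-sum. That is a real but small cost, because the clinical question is directional.

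**Conclusion.** The point holds conditionally. Section 11 names only chi-squared for categorical variables, and for graded items that test ignores order. Given 3 to 5 grades, 10 patients per group and a proportional shift of OR 3 to 8, the ordinary test gives up roughly a fifth to three fifths of the rank-sum power. The loss is smaller with exact tests and nil for yes/no items. The number of grades, the distributions and the odds ratios are all assumptions.

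Only secondary outcomes are touched. A reader might also infer an inflated error rate or a threat to the visual acuity results; neither follows. It is worth correcting because a more suitable test uses the same data.

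**What to change.** In section 11, replace the sentence on categorical variables with wording to this effect:

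*Ordered questionnaire answers (for example severity of halo or glare, frequency of spectacle use) will be compared between the lens groups, one answer per patient, with the two-sample Wilcoxon rank-sum (Mann-Whitney) test, exact or corrected for ties. Yes/no items will be compared with Fisher's exact test, because expected counts below 5 are likely. The chi-squared test will be used only for unordered variables with adequate expected counts.*

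In the preceding sentence, change the Wilcoxon *rank sign* test to the Wilcoxon *rank-sum* test. In section 7, name the questionnaire and give its response scale, so that the test for each item is fixed before the answers are seen.

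The cost is a few sentences, with no extra patients or data. There are two trade-offs. The rank-sum test is less sensitive to a difference in spread without a shift. Fisher's test is conservative: in the same enumeration, for an evenly split yes/no item at OR 5, its power is 17% against 31.5% for the ordinary chi-squared test, which is the price of an error rate that does not rely on a large-sample approximation.
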